4.4.4. Study withdrawal

A patient may be discontinued early from the study for the following reasons:

- Withdrawal by patient (specify reason in the eCRF)
- Lost to follow-up
- Death
- Physician decision (i.e. investigator decision based on protocol deviation, assessment that it is not in the patient's best interest to continue, or other reason [specify reason in the eCRF]).
- Sponsor decision (specify reason in the eCRF)

If the patient withdraws consent for disclosure of future information, the sponsor may retain and continue to use any data collected before such a withdrawal of consent. Additionally, patients may request destruction of any samples taken and not tested, and the investigator must document this in the site study records. Refer to the Schedule of Assessments ([Appendix 5](#)) for data to be collected at the time of study discontinuation and follow-up and for any further evaluations that need to be completed. Patients will be asked to complete Follow-up/EOS evaluations.

4.4.5. Lost to Follow-up

A patient will be considered lost to follow-up if he/she repeatedly is unable to be contacted by the study site after hospital discharge.

The following actions must be taken if a patient repeatedly is unable to be contacted:

- The site must attempt to contact the patient and reschedule the missed visit as soon as possible, counsel the patient on the importance of maintaining the assigned visit schedule, and ascertain whether or not the patient wishes to and/or should continue in the study.

- In cases in which the patient is deemed lost to follow-up, the investigator or designee must make every effort to regain contact with the patient (where possible, 3 telephone calls and, if necessary, a certified letter to the patient's last known mailing address or local equivalent methods). These contact attempts should be documented in the patient's medical record.
- Should the patient continue to be unreachable, he/she will be considered to have withdrawn from the study with a primary reason of lost to follow-up.

4.4.6. Replacement procedures

Patients who discontinue from the study will not be replaced.

4.4.7. Follow-up of patients who withdraw from the study

Due to the continued scientific importance of patient data even if study treatment is discontinued early, patients who withdraw from the study will be asked to complete final study procedures (Follow-up/EOS visit), as described in the Schedule of Assessments ([Appendix 5](#)). Patients who are no longer hospitalized may complete their assessments by telephone or via telemedicine or other means of remote communication.

All SAEs that are ongoing at the time of discontinuation, or that develop prior to the final Follow-up/EOS visit, will be followed until resolution or stabilization, or up to 30 days following the last dose of study treatment, by Covance Patient Safety Services (PSS) group ([Section 7.2.1.2](#)).

Steps will be taken by the sites to ascertain vital status in all randomized patients (eg, with a vital records search) up to Day 28.

4.5. Stopping Rules

The study will consist of a sentinel cohort of 20 patients (10 patients randomized to antroquinonol and 10 patients to placebo), and an expansion cohort of 154 patients (77 patients in each treatment group). Enrollment will pause after the 20th patient in the sentinel cohort has started treatment. Once the 20th patient in the sentinel cohort has completed 14 days of treatment, the unblinded DMC will assess the safety, efficacy, tolerability, and PK of study medication (interim analysis 1). The DMC will issue a recommendation to enroll patients for the expansion cohort, or to stop the study depending on the safety and futility assessment.

Once the 80th patient has been enrolled, and completed 14 days of treatment, the DMC will review the safety, tolerability and efficacy data (interim analysis 2). Enrollment may be restricted at the 100th patient until the DMC has completed the assessment to prevent excessive enrolment. The DMC will continue to review safety and assess the risk/benefit profile on an ongoing basis.

The following nonbinding rules will be considered by the DMC for futility, and the DMC will not make any recommendations to stop for early efficacy:

- Interim analysis 1 (sentinel cohort): An odds ratio of 3.5 or higher on the primary endpoint (proportion of patients who are alive and free of respiratory failure on Day 14) in favor of placebo.
- Interim analysis 2: An odds ratio of 1.2 or higher on the primary endpoint (proportion of patients who are alive and free of respiratory failure on Day 14) in favor of placebo.

Enrollment will pause pending unscheduled DMC review of safety data when any of the following criteria is met:

- ≥ 2 patients experience treatment-related SAE, or
- ≥ 2 patients experience treatment-related severe AEs that are of a similar nature.

Enrollment and dosing may restart following review of relevant safety data by the DMC.

A DMC Charter, which includes detailed processes, will be prepared.

4.6. Study Termination

The sponsor reserves the right to close a study site or terminate the study (ET of study) at any time for any reason at the sole discretion of the sponsor. Study sites will be closed upon study completion. A study site is considered closed when all required documents and study supplies have been collected and a study site closure visit has been performed. Reasons for study termination may include, but are not limited to:

- The discovery of an unexpected, significant, or unacceptable treatment-emergent safety risk to the patients
- Medical or ethical reasons affecting the continued performance of the study
- Difficulties in the recruitment of patients
- Cancellation of drug development.

The investigator may initiate study site closure at any time, provided there is reasonable cause and sufficient notice is given in advance of the intended termination. Reasons for the early closure of a study site by the sponsor or investigator may include, but are not limited to:

- Failure of the investigator to comply with the protocol, the requirements of the Institutional Review Board/Ethics Committee or local health authorities, the sponsor's procedures, or Good Clinical Practice guidelines
- Inadequate recruitment of participants by the investigator.

5. STUDY TREATMENTS

5.1. Treatments Administered

Details on the active treatment and placebo provided to patients are summarized in [Table 1](#).

Table 1: Treatment Details

Study Treatment Name:	Antroquinonol (Hocena [®])	Placebo
Dosage Formulation:	Antroquinonol in corn oil, encapsulated volume 212 µL, in a gelatin capsule	Corn oil, encapsulated volume 212 µL, in a gelatin capsule
Unit Dose Strength(s)	100 mg	N/A
Dosage Level(s):	One capsule BID (200 mg total daily dose)	One capsule BID
Route of Administration:	Oral	Oral
Dosing Instructions:	To be taken every 12 hours approximately within 15 minutes after a meal or refreshment to reduce gastrointestinal adverse effect	To be taken every 12 hours approximately within 15 minutes after a meal or refreshment for consistency with active treatment
Packaging and Labeling:	Antroquinonol will be provided in a polyethylene bottle. Each bottle will be labeled as required per country regulations.	Placebo will be provided in a polyethylene bottle. Each bottle will be labeled as required per country regulations.
Manufacturer:	Golden Biotechnology Corporation	Golden Biotechnology Corporation

Abbreviations: BID = twice daily.

5.1.1. Antroquinonol

The physicochemical properties and the pharmaceutical specifications of antroquinonol are provided in the IB.⁵

Antroquinonol is supplied by Golden Biotechnology Corporation. Antroquinonol (100 mg in corn oil, encapsulated volume 212 µL) will be filled in #2 gelatin capsules and then packed in a light-protected polyethylene bottle and closed with a piece of polyethylene cap liner fitted in the cap for dispensation at each visit. The study treatment will be labeled in accordance with country-specific requirements.

Beginning on Day 1, patients in the sentinel cohort who are randomized to receive active treatment will receive 1 capsule of study treatment (100 mg antroquinonol) orally BID. Antroquinonol should be taken approximately within 15 minutes after a meal or refreshment to reduce any gastrointestinal adverse effect.

5.1.2. Placebo

Placebo is supplied by Golden Biotechnology Corporation and will be in similar packaging as described for antroquinonol in [Section 5.1.1](#).

Placebo (corn oil, encapsulated volume 212 μ L) will be filled in #2 gelatin capsules and then packed in a light-protected polyethylene bottle and closed with a piece of polyethylene cap liner fitted in the cap for dispensation at each visit. The study treatment will be labeled in accordance with country-specific requirements.

Beginning on Day 1, patients who are randomized to receive placebo treatment will receive 1 capsule of placebo orally BID. Placebo capsules should be taken approximately within 15 minutes after a meal or refreshment to reduce any gastrointestinal adverse effect. Dosage of placebo will match dosage of antroquinonol.

5.2. Preparation, storage, handling, and accountability

Antroquinonol and placebo will be supplied by Golden Biotechnology Corporation for final formulation and packaging; along with the batch/lot numbers and Certificates of Analysis. The study treatment will be provided as individual patient kits consisting of 1 bottle with 30 capsules (supply for dosing 1 capsule BID for 14 days, plus 2 extra capsules). The sponsor is responsible for shipping both the treatments to the study site and for implementing strict inventory control for drug accountability. During shipping, antroquinonol will be packaged to maintain a temperature below 27°C/80.6°F.

The study investigator and/or designee must confirm appropriate temperature conditions have been maintained during transit for all study treatment received and any discrepancies are reported and resolved before use of the study treatment. Drug accountability and inventory (capsule counts) will be recorded in the eCRF and the relevant study log.

All study treatments must be stored in a secure, environmentally controlled, and monitored (manual or automated) area in accordance with the labeled storage conditions with access limited to the investigator and authorized site staff.

Only patients enrolled in the study may receive study treatment and only authorized site staff may supply or administer study treatment. The investigator, institution, or the head of the medical institution (where applicable) is responsible for study treatment accountability, reconciliation, and record maintenance (ie, receipt, reconciliation, and final disposition records).

Further guidance and information for the final disposition of unused study treatment are provided in a separate document.

5.3. Method of treatment assignment

All patients will either receive antroquinonol or placebo after randomizing in a 1:1 ratio using an Interactive Web Response System (IWRS). Before the study is initiated, the log in information and directions for the IWRS will be provided to each site.

Randomization will be stratified by remdesivir or other authorized treatments for COVID-19 use at baseline and age at baseline (≤ 65 years vs > 65 years).

Patients confirmed eligible at screening will be assigned a patient identifier prior to the administration of study treatment. The patient identifier will consist of the country number, site number, and patient number. The country number will comprise the first 2 digits, the site number will comprise the next 3 digits, and the patient number will comprise the final 3 digits eg, 01002003 is Country 1, Site 2, Patient 3.

Study treatment will be dispensed at the Day 1 visit (see Schedule of Assessments, [Appendix 5](#)).

5.4. Dose Modification

No modification of study treatment dosage for patient management will be permitted.

5.5. Blinding

This is a double-blind study.

The IWRS will be programmed with blind-breaking instructions. The study blind may be broken if, in the opinion of the investigator, it is in the patient's best interest to know the study treatment assignment. The sponsor and the Contract Research Organization (CRO) must be notified before the blind is broken unless identification of the study treatment is required for a medical emergency in which the knowledge of the specific blinded study treatment will affect the immediate management of the patient's condition (eg, antidote is available). In this case, sponsor and the CRO must be notified within 24 hours after breaking the blind. The date and reason that the blind was broken must be recorded in the source documentation and eCRF, as applicable.

5.6. Treatment Compliance

Records shall be maintained of the delivery of study treatment to the study sites, the inventory at the study sites, the use for each patient, and the return to the sponsor.

These records shall include dates, quantities, batch/lot information, expiry dates, and the unique code numbers assigned to the study treatment and study patients.

The investigator shall be responsible for ensuring that the records adequately document that the patients were provided the doses specified in the protocol and that all study treatment received from the sponsor is reconciled.

Site staff will monitor compliance of patients with their assigned randomized treatment (antroquinonol or placebo) by recording the number of capsules actually used.

Patients will be administered treatment by the site staff during hospitalization. On discharge, all patients are to be reminded of the importance of compliance with the treatment with an emphasis on taking their study treatment on schedule and contacting the study site for an appointment as soon as possible if they think they are experiencing worsening of condition. Compliance

information will be captured via eSource (if a patient version is used) or telemedicine. Patients will return unused supply at the EOT visit.

6. PRIOR AND CONCOMITANT THERAPIES AND OTHER RESTRICTIONS

6.1. Permitted medications

Any medication or vaccine (including over-the-counter or prescription medicines, vitamins, and/or herbal supplements) that the patient is receiving at the time of enrollment or receives during the study must be recorded in the eCRF along with:

- reason for use
- dates of administration including start and end dates, and
- dosage information including dose and frequency.

Patients must be instructed not to take any medications, including over-the-counter products, without first consulting with the investigator. The Medical Monitor should be contacted if there are any questions regarding concomitant or prior therapy.

Medications, other than those listed as prohibited medications and other restrictions, which are considered necessary for the patient's safety and well-being, may be given at the discretion of the investigator and must be recorded in the appropriate sections of the eCRF.

6.2. Prohibited medications

Simultaneous participation in other clinical treatment study protocols is not allowed.

Treatment with any antiviral drugs (except remdesivir or other authorized treatments for COVID-19), or with any drugs known to be strong inhibitors or inducers of CYP2C19, 3A4, 2C8, and 2E1 are prohibited within 14 days or 5 half-lives prior to the start of study treatment. Drugs with a narrow therapeutic index that are substrates of 1A2, 2B6, 2C8, 2C9, 2C19, 3A, and 2D6 are also prohibited.

A list of commonly known CYP inducers and inhibitors is given in [Appendix 6](#) for reference use.

Antroquinonol is a purified compound from an extract of *A. camphorata*. For this reason, the use of *A. camphorata*-containing products is prohibited within 2 weeks prior to the first administration of study drug, and the use of *A. camphorata*-containing products other than antroquinonol is prohibited throughout the study.

Patients who begin to receive nonstudy antiviral medication after the start of study treatment will be discontinued from study treatment. Note: remdesivir or other authorized treatments for COVID-19 is allowed if considered SoC, if started prior to randomization or during the study. Initiation of remdesivir or other authorized treatments for COVID-19 during the study will be considered a treatment failure if started due to progression of disease.

Administration of an authorized COVID-19 vaccines is permitted as per the local health authority recommendation.

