Patients will undergo assessment during hospitalization or could be discharged after start of study treatment any time after Day 2 if judged to be ready for discharge. If discharged, patients will then be requested to take study treatment at home (as prescribed) up to Day 14. End of Treatment assessments at Day 14 (+2 days) (at home or site visit) will be performed. A Day 5 (+/- 1 day) visit (at home or site visit) will be performed if the patient is discharged prior to Day 5. If the patient is discharged after completion of treatment and before the follow-up visit, he/she will be followed up on Day 28 (± 2 days) for study assessments (a telephone or telemedicine visit). Post discharge, assessments will be done by telephone or telemedicine, except for Day 5, Day 14, and Early Termination (ET) of Study Treatment. If the discharge, ET, or Early Withdrawal visit falls within the window of a scheduled Day visit, the assessments for the visits can be combined as one visit. On days of laboratory assessments, discharged patients will have a home visit. On days of no laboratory assessments, discharged patients will complete their assessments via telephone, telemedicine, or other means of remote communication. Additionally, patients will receive a diary to capture all doses after a discharge.

Number of patients:

A total of 174 patients are planned to be randomized into the study:

- 20 patients in the sentinel cohort (10 patients in each treatment group)
- 154 patients in the expansion cohort (77 patients in each treatment group).

This enrollment level ensures 80% power to demonstrate proof of concept efficacy with one-sided alpha of 0.2.

The sample size is based on the following assumptions:

- The randomized allocation ratio is 1:1 between the antroquinonol group and the placebo group
- The proportion of patients alive and free of respiratory failure is approximately 78% on placebo vs 89% on antroquinonol
- The following nonbinding rules will be considered by the DMC for futility, and the DMC will not make any recommendations to stop for early efficacy:
 - Interim analysis 1 (sentinel cohort): An odds ratio of 3.5 on the primary endpoint in favor of placebo.

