4.4.2. Hepatic injury or renal impairment

4.4.2.1. *Hepatic injury*

Discontinuation of study treatment for abnormal liver tests should be considered by the investigator when a patient meets one of the conditions outlined in [Figure 2](#) or if the investigator believes that it is in the best interest of the patient.

Figure 2: Stopping Criteria for Liver Injury

Abbreviations: ALT = alanine aminotransferase; INR = international normalized ratio; ULN = upper limit of normal
 Note: INR value is not applicable to patients on anticoagulants.

4.4.2.2. *Renal impairment*

If a patient has renal impairment (creatinine clearance <50 mL/min), treatment should be discontinued.

4.4.3. **Discontinuation of study treatment**

A patient may be discontinued early from study drug treatment (ET of study treatment) for the following reasons:

- Lack of efficacy (e.g. patients who require nonstudy antiviral or anticytokine therapy due to progression of COVID-19), and the investigator's decision. Note: remdesivir or other authorized treatments for COVID-19 is allowed if considered SoC, if started prior to randomization or during the study. Initiation of remdesivir or other authorized treatments for COVID-19 during the study will be considered a treatment failure if started due to progression of disease.
- Adverse event
- Withdrawal by patient (specify reason in the eCRF)
- Lost to follow-up
- Death

- Physician decision (i.e. investigator decision based on protocol deviation, assessment that it is not in the patient's best interest to continue, or other reason [specify reason in the eCRF]).
- Sponsor decision (specify reason in the electronic case report form [eCRF])

No temporary treatment discontinuation is permitted.

Patients who discontinue study treatment prematurely will be asked about the reason(s) for discontinuation and will be asked to continue all assessments up to Day 28. Patients will be educated about the continued scientific importance of their data and encouraged to complete the Day 28 Follow-up/EOS assessments even if they discontinue study treatment prematurely.

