## Statistical Analysis Plan

Sponsor Name: Golden Biotechnology Corporation  
Sponsor Protocol ID: GH Covid-2-001

Covance Study ID: 000000203201

Exclusion Criteria 12	patient requires frequent or prolonged use of systemic corticosteroids ( $\geq 20$ mg of prednisone/day or equivalent for $>4$ weeks) or other immunosuppressive drugs (e.g., for organ transplantation or autoimmune conditions).	Non-Programmable check of the prior medications.
Treatment Compliance	patient with study treatment compliance $<50\%$	Non-Programmable check the study treatment compliance based on drug accountability data.
Prohibited Medication or Therapy	patient has used prohibited medications or therapies documented in the protocol or identified by clinical or medical team	Non-Programmable check of the concomitant medication data.

As defined in the table, all important protocol deviations leading to exclusion from the PPS will be determined non-programmatically from the data. Those criteria which require clinical or medical monitoring interpretation will be reviewed prior to database lock.

All important protocol deviations leading to exclusion from the PPS occurring during the study will be reviewed and approved by Golden Biotechnology Corporation prior to database lock and unblinding. Should additional important protocol deviations leading to exclusion from the PPS, not anticipated at the time of preparing this SAP, be identified during the study (and prior to unblinding) they will be documented in a SAP amendment/Per Protocol Set Identification Plan, other document and included in all relevant protocol deviation reviews and approvals.

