#### 7.6.1 Primary Efficacy Analysis

The proportion of patients from each treatment group who are alive and free of respiratory failure on Day 14 will be summarized and compared using logistic regression, with treatment, remdesivir or other authorized treatments for COVID-19 use at baseline (yes vs no) and age at baseline ( $> 65$  years vs  $\leq 65$  years) as covariates. The p-value for treatment effect will be provided based on the Wald test. P-value based on Fisher's exact test will also be provided. Odds ratio along with its 95% confidence interval will be provided based on the exact method. In addition, the risk difference for the treatment effect and 95% confidence interval will be calculated based on the proportion of patients alive and respiratory failure free in the control group and the estimates of odds ratio, along with its 95% confidence interval.

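### The protocol calls authorised COVID-19 therapy started for progression a treatment failure, but no analysis applies this, and the per-protocol rules can drop patients because they progressed

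*Protocol*

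**What the plan says.** Protocol 6.2 allows remdesivir and other authorised COVID-19 treatments as standard of care, before or during the study. It adds that starting one during the study "will be considered a treatment failure if started due to progression of disease". Protocol 4.4.3 repeats the sentence under lack of efficacy, a reason for stopping study drug, where the example given is "patients who require nonstudy antiviral or anticytokine therapy due to progression of COVID-19". Under 6.2, a non-study antiviral leads to discontinuation of study treatment. Patients who stop are asked to continue assessments to Day 28.

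The primary endpoint does not mention rescue. SAP 7.6.1 reads: "The proportion of patients from each treatment group who are alive and free of respiratory failure on Day 14 will be summarized and compared". Protocol 7.1.2.6 defines respiratory failure by four supports: invasive ventilation, non-invasive ventilation, high-flow oxygen and ECMO. The only special status rule for this endpoint, in Protocol 8.3, concerns death.

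SAP 5.4.1 removes from the PPS any patient for whom this holds: "patient has used prohibited medications or therapies documented in the protocol". The row also covers drugs that the clinical or medical team identifies. Another row covers exclusion criterion 8, whose wording extends to concurrent use of other possible COVID-19 drugs but exempts authorised standard of care. A third removes patients with compliance below 50%. SAP section 8 declares no change in statistical methods from the protocol.

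**The concern.** The protocol gives one clinical event an explicit outcome status, and the analysis never uses it. Take a patient who worsens, is started on an authorised drug for that reason, and is on nasal oxygen on Day 14. Protocol 6.2 calls this a treatment failure; the primary model counts a success. The study rationale (Protocol 1.1) names prevention of disease progression among its goals, so the event bears on the question asked.

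If rescue is commoner on placebo and works, the Day 14 comparison understates the drug. If it is commoner on antroquinonol, the comparison credits the drug with what rescue achieved. No planned efficacy analysis counts rescue as failure. The PPS, meant as support, can remove patients because of a poor outcome after randomisation, which weakens it as a check.

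**Working it through.** **How each part of the plan treats therapy started for progression**

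- Protocol 4.4.3 and 6.2: treatment failure, for authorised therapy.
- ITT primary analysis (Protocol 8.4.1, SAP 7.6.1): decided only by vital status and the four supports on Day 14. Protocol 2.2 and SAP 3.1 introduce the supports as examples, but Protocol 7.1.2.6 lists them as the definition, and no drug is among them. Success scoring follows from this and from the absence of a rescue rule; no sentence states it outright.
- Missing-data rules (Protocol 8.3, SAP 6.2): no mention of rescue.
- Clinical-improvement time-to-event analyses (SAP 7.6.2.1): run twice, once censoring at new authorised therapy and once ignoring it. Neither counts rescue as failure.
- Exploratory analysis (SAP 3.3, 7.6.3): an interaction term for new authorised standard-of-care treatments, without separating use for progression.

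**Routes out of the PPS (SAP 5.4.1)**

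1. Prohibited medication. This reaches non-study antivirals. Protocol 6.2 does not name anticytokine drugs, so under this row their removal depends on the clinical or medical team identifying them.
2. Exclusion criterion 8. The wording reaches concurrent use of other possible COVID-19 drugs. The stated check is of prior medications only, so this is the least certain route.
3. Compliance below 50%. SAP 7.7.1 ends the expected dosing period at end of treatment only for stops due to adverse event, death, physician decision or sponsor decision. Lack of efficacy is a separate reason in Protocol 4.4.3. For it, expected capsules run to Day 14 or end of study, whichever is first. For a patient still in the study on Day 14, expected = 2 × 14 = 28, so fewer than 14 capsules taken is below 50%. Stopping after 10 capsules gives 10/28 = 36%. This row does not ask which drug was used, so it can also remove a patient rescued with authorised therapy who stops study drug for lack of efficacy.

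**The plan's own power figure**

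The protocol synopsis gives the inputs. Size: "A total of 174 patients are planned to be randomized into the study". Allocation: "The randomized allocation ratio is 1:1 between the antroquinonol group and the placebo group", hence 87 per arm. Rates: "The proportion of patients alive and free of respiratory failure is approximately 78% on placebo vs 89% on antroquinonol". Claim: "This enrollment level ensures 80% power to demonstrate proof of concept efficacy with one-sided alpha of 0.2".

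The formula is power = Φ(log OR / SE − 0.8416), with SE² = 1/(87·p₀(1−p₀)) + 1/(87·p₁(1−p₁)).

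For 78% vs 89%, log OR = 0.825 and SE = 0.429, so power = Φ(1.921 − 0.842) = 86%. The final boundary exp(−0.8416 × 0.4294) = 0.697 matches Protocol 8.1. With both futility rules obeyed, power is 80.1% by binomial simulation and 81.2% by normal approximation, which reproduces the stated 80%.

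**Scoring rescue as failure**

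The documents give no rescue rate, so the rates below are assumptions. They are percentages of all patients in the arm who are rescued and would otherwise be Day 14 successes. Rescued patients on one of the four supports on Day 14 already fail and change nothing. Power is for a fixed design without futility looks, 87 per arm, one-sided 0.2.

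| Rescued, placebo / active | Composite success, placebo vs active | Difference | Power |
|---|---|---|---|
| none | 78% vs 89% | 11 points | 86% |
| 5% / 2.5% | 73% vs 86.5% | 13.5 points | 91% |
| 10% / 5% | 68% vs 84% | 16 points | 94% |
| 5% / 10% | 73% vs 79% | 6 points | 53% |

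For the last row, log OR = 0.330 and SE = 0.357, so power = Φ(0.925 − 0.842) = 53%.

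Equal rescue also matters. Rescoring 10% of Day 14 successes in each arm gives 0.78 × 0.9 = 70.2% vs 0.89 × 0.9 = 80.1%, with power 75%.

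**The case against.** The strongest reply is that treatment failure is a disposition label. In Protocol 4.4.3 the sentence sits among reasons for stopping study drug, no endpoint refers to it, and SAP 7.2 tabulates discontinuation reasons by arm, so an imbalance in lack-of-efficacy stops would be seen. This may be what was intended. But 6.2 repeats the sentence outside that list and neither place limits it, so the documents should say so.

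A second reply is that Day 14 status regardless of rescue is a recognised ITT question, supported by continued follow-up. That stands: the primary endpoint need not change.

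Third, rescue is not wholly ignored. The two censoring rules address it for clinical improvement, and the supportive mITT set keeps these patients. That also stands, although none of these analyses counts rescue as failure.

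A reader might infer something stronger: that one event is a failure in the protocol, a success in the ITT analysis and absent from the PPS. The documents do not support this as a general statement. The failure sentence covers authorised therapy, which the criterion-8 row exempts; the medication rows reach mainly non-authorised drugs. The two meet only in the compliance row, and only if study drug stops early for lack of efficacy.

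**Conclusion.** The point holds in two parts. First, an explicit protocol statement about authorised therapy for progression has no effect in any analysis, and the primary analysis can count such a patient as a success. Second, three PPS rows can drop patients because they progressed, with the compliance row able to reach authorised rescue as well.

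Its size is conditional. Across the assumed rescue rates, composite power runs from 53% to 94% against 86%, and the difference from 6 to 16 points against 11. The direction depends on which arm is rescued more, which the documents do not say. A reader might take these figures as a loss of power for the trial as planned. They are not: they describe a supplementary composite, and power for the primary endpoint is unchanged. Nor do they show that the primary analysis is invalid or biased in a known direction. The matter deserves correction because it is a plain inconsistency and cheap to settle.

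**What to change.** Reconcile Protocol 4.4.3 and 6.2 with the SAP by stating whether treatment failure is a disposition label or an analysis rule. Then:

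1. Keep Day 14 status as the primary endpoint. In SAP 7.6.1 add one supplementary analysis with the same logistic model. It counts as failure any patient who, before Day 14, starts COVID-19 therapy for progression or stops study drug for lack of efficacy. Identify these patients under blind from the recorded reason for use and dates (Protocol 6.1) and the discontinuation reason.
2. In SAP 5.4.1 state that therapy started after randomisation for progression, and low compliance caused by a lack-of-efficacy stop, do not exclude a patient from the PPS. Apply this to the prohibited-medication, exclusion-criterion-8 and compliance rows together. Amending only the first would leave the other two able to remove the same patients.

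The cost is SAP wording and one more run of an existing model. There is a small downside: whether a drug was started because of progression is an investigator judgement, and a generic reason for use may not separate progression from COVID-19 itself, so a blinded review before unblinding may be needed. Who receives rescue is not changed.
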